Study aims and primary and secondary outcomes

The study has three aims.

1. Among 450 (18-24 y.o) JIY in BJI randomized to either Link2CARE or standard of care (SOC), to determine **the efficacy of Link2CARE** delivered by STAY staff embedded within BJI on (a) HIV outcomes: HIV testing/repeat testing; HIV risk behaviors; (b) STI outcomes: STI testing/repeat testing; linkage to care of JIY with STIs; (c) SU outcomes: SU screening; SU; linkage to care of JIY with SU/D; and (d) (exploratory) linkage to care of HIV+ youth and linkage to PrEP for (behaviorally) eligible HIV- youth.
2. To determine **the influence of theoretically-based mechanisms of change of Link2CARE** (e.g., predisposing characteristics, enabling resources, perceived need, organizational climate; staff attitudes) on the proposed HIV, STI and SU outcomes.
3. To describe Link2CARE implementation and elucidate the **system/organizational-, staff-, and youth-level factors that influence implementation (i.e. acceptability, sustainability, feasibility) of Link2CARE in an ASP** to develop a plan for dissemination and scale-up of Link2CARE in New York City

The study has the following primary, secondary, and exploratory outcomes (related to aim 1)

Domain 1 (primary outcomes: HIV outcomes): (a) total number of unprotected anal and vaginal sex occasions in past three months at 12 month FU; (b) acceptance of HIV testing at initial offering (y/n), (c) any HIV

testing between 6-month and 12-month FU (y/n).

Domain 2 (secondary outcomes: SU outcomes): (a) frequency of youth substance use in past 30 days at 3-, 6- and 12-month FUs; (b) number of youth referred to SU treatment at 3-, 6- and 12-month FUs; at (c) number of youth attending intake plus one treatment session at 3-, 6- and 12-month FUs.

Domain 3 (secondary outcomes: STI testing outcomes): (a) acceptance of STI testing at initial offering (y/n), (b) any STI testing between 6-month and 12-month follow up; (c) number of STI+ youth referred to STI treatment at 3, 6, and 12 months FUs; (d) number of STI+ youth attending ≥ 1 treatment appointment at 3, 6, 12 months FUs.

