Domain 4 (exploratory outcomes: HIV/PrEP linkage outcomes): (a) number of HIV+ youth referred to HIV treatment at 3, 6, and 12 months FUs, (b) number of HIV+ youth attending at least one treatment appointment at 3, 6, and 12 months FUs; (c) number of youth behaviorally PrEP eligible referred to PrEP/medical care at 3, 6, and 12 months FUs, (b) number of youth behaviorally PrEP eligible attending at least one HIV care appointment care at 3, 6, and 12 months FUs.

TRIAL MANAGEMENT

Study/data collection sites

Data will be collected at **Brooklyn Justice Initiative (BJI), run by Center for Court Innovation**. BJI is an alternative sentencing program (ASP) for JIY processed through Brooklyn Criminal Court. BJI aims to reduce re-offending and increase public safety; promote use of meaningful social services; provide rigorous compliance monitoring; and reduce criminal convictions and use of jail. Located in the Brooklyn Criminal Courthouse, BJI serves 9,000 youth/year; almost all (94%) are mandated to BJI for ≤ 15 days.

Study sample description

To address the study aims we will collect data from a sample of youth aged 18-24 who have been placed in BJI (sample 1), from a sample of HIV testing outreach staff (sample 2) and from staff at BJI (Sample 3).

Sample size and power

The total sample size of sample 1 will comprise N=472 youth currently enrolled at BJI: n=14 youth will serve on an advisory panel to provide feedback as MOVE and NYSBIRT are adapted; n=8 youth will pilot test the adapted Link2CARE protocols prior to the efficacy test of Link2CARE; and n=450 youth will be randomly assigned (1:1) to either Link2CARE or standard of care. Sample 2 will comprise N=2 Project STAY outreach workers who will be embedded at BJI and will deliver all elements of Link2CARE to youth. Sample 3 sample size is expected to be all 15 staff who work at BJI.

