HIV and STI testing: Following randomization and baseline assessment, all youth will be offered an HIV and an STI test for Chlamydia and gonorrhea; initial testing will take place onsite at BJI. All youth will also be offered HIV and STI testing at each follow-up interview (3m, 6m and 12m). **HIV testing** will be done using Oraquick advance rapid HIV test. Following brief pre-test counseling, an oral swab will be used to collect saliva to conduct HIV rapid test. Once conducted, the embedded Project STAY staff member (LINK2CARE condition) or human subjects-trained RA (standard of care) will provide results to the participant and HIV+ JIY will be immediately linked to care following Link2CARE linkage protocols. The Project STAY staff or RA will then place the swab in a closed Developer Solution vial, then back into the package. The entire package will be placed in a baggie. The baggie with the used test will be brought back to NYSPI by human-subjects trained RAs and turned in to the Project Director who will enter the results into a the project database at NYSPI that is held on a secure server. The baggie containing the used OraQuick test and materials will then be disposed of in the appropriate waste container. Staff (interviewers and office staff) will wear gloves when manipulating test materials. **STI testing** will occur by the collection and processing of the urine specimens using a Gen-probe APTIMA Urine Specimen Collection Kit for Male and Female Urine Specimens. The testing kits are provided and the urinalysis will be performed by the New York City Department of Health (NYCDOH) at no cost as part of an ongoing agreement with Project STAY. The client is instructed about how to provide the urine sample, and is sent to the bathroom by either the embedded Project STAY staff member (LINK2CARE condition) or human subjects-trained RA (standard of care). Upon return, the Project STAY staff member or RA packages the sample and arranges for pickup by the Department of Health's (DOH) Bureau of STD control. NYCDOH uses the third generation nucleic acid amplification test (NAAT), yielding qualitative testing results. Specimens will be collected and transferred into their respective specimen transport tubes. The transport solutions in these tubes release the rRNA targets and protect them from degradation during storage. When the APTIMA Combo 2 Assay is performed in the laboratory, the target rRNA molecules are isolated from specimens by the use of capture oligomers in a method called target capture. After the target capture steps are completed, the specimens are ready for amplification. The GEN-PROBE APTIMA Combo 2 Assay replicates a specific region of the 23S rRNA from CT and a specific region of the 16S rRNA from GC via DNA intermediates. A unique set of primers is used for each target molecule. Differences in the kinetic profiles of the CT and GC labeled probes allow for the differentiation of signal; kinetic profiles are derived from measurements of photon output during the detection read time. The chemiluminescent detection reaction for CT signal has very rapid kinetics and has the "flasher" kinetic type, while the detection reaction for GC signal is relatively slower and has the "glower" kinetic type. Assay results are determined by a cut-off based on the total RLU and the kinetic curve type. Written documentation of the test results will be obtained by the research office from the NYCDOH Microbiology laboratory within 7 days after the urine sample was delivered. The Project Director who will enter the results into a the project database at NYSPI that is held on a secure server Respondents randomized to Link2CARE who test positive will be informed by embedded Project STAY staff of their results and will immediately be linked to care by STAY staff following Link2CARE linkage protocols. Respondents randomized to SOC who test positive will be contacted by study staff using a succession of methods (telephone, registered letter, and, if refused or undelivered, regular mail). Participants will be informed that antibiotics are used to treat Chlamydia and Gonorrhea. We will counsel that all sex partners within the last 60 days should be evaluated and treated and to avoid sex until they and their partners have been treated for at least 7 days or 7 days after a single dose treatment. Specific referral procedures will be followed to maximize chances that participants will seek treatment.

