Analysis plan for Specific Aim 1. Prior to conducting our multivariable analyses, we will examine study variables using descriptive statistics, testing for differences across demographic characteristics (e.g., race/ethnicity, age) using t-tests, ANOVAs, and Chi-squares, as appropriate. Systematic baseline differences are not expected; however, any parameters that differ across conditions at baseline will be included as covariates in subsequent models. We will calculate descriptive summary statistics corresponding to study variables at each follow-up (FU) to understand any temporal patterns, as well as compare the two groups in terms of average change from baseline to 12-months post-baseline. We will use the general framework of generalized linear models (GLM) to model the longitudinal outcome trajectories and GEE method to account for within-subject correlation across the four time points (baseline, 3-, 6-, and 12-months). Stratified randomization of participants to the groups based on their gender requires that the analysis also include gender as covariate. The general form of the analysis model will be $g(\mu) = \alpha_0 + \alpha_1 X + \beta I + \sum \gamma_i T_i + \sum \delta_i T_i I$, where g denotes the link function (identity for continuous outcome, logit for binary outcome and natural log for count outcomes) X represents the indicator of female (vs. male), I is the group indicator for Link2CARE (vs. SOC), and T_i is the indicator for time at 3-month, 6-month, and 12-month evaluation (vs. baseline) for $i=1, 2, \text{ and } 3$. The interaction coefficients δ_i are of interest, measuring the difference in the rate of change in outcome across the two treatment groups at each follow-up assessment. We will employ the above analytic approach to examine differences between youth in Link2CARE and in the SOC condition with respect to key study parameters within these four domains detailed below. Proposed hypotheses are that the experimental arm (Link2CARE) would have better outcomes (e.g. greater reduction on total number of unprotected anal and vaginal sex occasions in past three months from baseline to 12 month FU; greater increase in proportion of acceptance of HIV testing at initial offering; greater reduction on frequency of substance use in past 30 days at 3-, 6- and 12-month FUs; and of those referred to SU treatment, a greater number of youth attending intake plus one treatment session at 3-, 6- and 12-month FUs)

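### As written, HIV-positive youth in both arms are linked by the Link2CARE protocols, so the exploratory arm comparison of HIV linkage has no linkage contrast; the STI contrast is diluted but remains

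*Combined protocol and SAP*

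**What the plan says.** Outcome numbers follow the section on study aims and outcomes, where Domain 3 is STI and Domain 4 is HIV/PrEP linkage. The Aim 1 analysis plan lists these two domains in the opposite order.

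- **HIV-positive youth.** Under Data acquisition, entry and transmission (Phase 2, HIV and STI testing), one sentence covers both arms. It names the embedded Project STAY worker for Link2CARE, and continues "or human subjects-trained RA (standard of care) will provide results to the participant and HIV+ JIY will be immediately linked to care". The closing clause in full is "HIV+ JIY will be immediately linked to care following Link2CARE linkage protocols".
- **STI-positive youth.** The same section separates the arms here. Link2CARE positives are told and linked at once by the embedded worker. For the comparator, "Respondents randomized to SOC who test positive will be contacted by study staff using a succession of methods": telephone first, then registered letter, then ordinary mail. After counselling text comes "Specific referral procedures will be followed to maximize chances that participants will seek treatment", with no limit by arm.
- **Outcomes.** Aim 1(b) asks for efficacy on "linkage to care of JIY with STIs", and Aim 1(d), exploratory, on linkage of HIV-positive youth. Domain 3 (secondary) includes "c) number of STI+ youth referred to STI treatment at 3, 6, and 12 months FUs", followed by attendance at one or more appointments (3d). Domain 4 (exploratory) includes "a) number of HIV+ youth referred to HIV treatment at 3, 6, and 12 months FUs", followed by attendance (4b).
- **Analysis.** The Aim 1 plan applies its arm-by-time model to "examine differences between youth in Link2CARE and in the SOC condition with respect to key study parameters within these four domains".

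**The concern.** The brief protocol description lists linkage to care as one of the three components of Link2CARE. A comparison of linkage between arms tests that component only if the comparator does not receive it. As written, HIV-positive youth in the standard-of-care arm do receive it. A null result on 4(a) or 4(b) would then say nothing about whether the protocol works, and a difference in counts could be reported as linkage efficacy when it only shows that one arm found more positives.

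For STI, the comparator is study-run testing, notification and referral, not usual care. The plan does not say so where it sets out the comparison. A count of STI-positive youth referred also combines how many accepted a test with how many positives were then referred, so it cannot be read as a linkage effect alone.

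**Working it through.** **Plan's own figure.** The plan gives no rate or power for any linkage outcome. Its power statement covers primary outcomes only, and it reproduces: Φ(0.35 × √(169/2) − 2.394) = 0.795, against 80% stated. If 2% of the comparator arm received the full effect (an assumption), this becomes Φ(0.35 × 0.98 × √(169/2) − 2.394) = 0.776.

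**Step 1: what each arm receives after a positive test.**

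| | Link2CARE | Standard of care | Contrast among positives |
|---|---|---|---|
| HIV+ | Link2CARE linkage protocols | Link2CARE linkage protocols | None, as written |
| STI+ | Immediate linkage by the embedded worker | Staff contact by phone or letter, then referral procedures | Reduced, but present |

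**Step 2: what a count measures.** Take 225 youth per arm (450 randomized 1:1) and one round of testing:

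expected count referred = 225 × acceptance × positivity × referral.

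With equal positivity, the arm ratio is (acceptance ratio) × (referral ratio). Acceptance, positivity and referral rates are not in the documents, so those below are assumptions. With acceptance 80% v 60% and all positives referred in both arms:

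| STI positivity | Link2CARE | Standard of care | Ratio |
|---|---|---|---|
| 5% | 9.0 | 6.8 | 1.33 |
| 10% | 18.0 | 13.5 | 1.33 |
| 15% | 27.0 | 20.2 | 1.33 |

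The ratio is 0.80/0.60 at any positivity, with no linkage effect. At equal acceptance it is 1.00. The same formula applies to the HIV counts in 4(a) and 4(b).

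Attendance per youth randomized behaves alike. With 10% positivity and 60% attendance among positives in both arms, 225 × 0.80 × 0.10 × 0.60 = 10.8 against 225 × 0.60 × 0.10 × 0.60 = 8.1, again 1.33. Replacing 3(c) by 3(d) would therefore not separate linkage from test uptake.

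**Step 3: number of HIV-positive youth.** With acceptance of 50% to 90% and 0.5% to 2% positive, the range is 225 × 0.5 × 0.005 = 0.6 to 225 × 0.9 × 0.02 = 4.1 per arm. Tests offered at follow-up could add a few. With 3 per arm, even a 3 v 0 split gives a two-sided Fisher p of 2/20 = 0.10.

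**Step 4: how far the STI contrast is diluted.** STI-positive youth per arm: 225 × 0.5 × 0.05 = 5.6 (low), 225 × 0.7 × 0.10 = 15.8 (middle), 225 × 0.9 × 0.15 = 30.4 (high). The table gives the power of a two-sided Fisher test at 0.05 for the proportion referred among positives. It is the exact binomial sum over significant tables, with Link2CARE referral assumed at 95%.

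| Standard-of-care referral | 6 per arm | 16 per arm | 30 per arm |
|---|---|---|---|
| 90% | 0.00 | 0.01 | 0.02 |
| 70% | 0.01 | 0.31 | 0.63 |
| 60% | 0.03 | 0.57 | 0.89 |
| 40% | 0.18 | 0.91 | 1.00 |

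The contrast disappears only if study-run referral reaches nearly every comparator positive. The documents do not state how many it will reach.

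**The case against.** The HIV sentence may be loose drafting meant for Link2CARE only, and the linkage protocols, which might set out a comparator pathway, are not reproduced in this document. That is possible. But the sentence names the standard-of-care result-giver, the STI text shows that the authors separate the arms when they mean to, and nothing here gives another pathway. If it is loose drafting, the comparator pathway for HIV-positive youth still has to be written.

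The HIV comparison is also exploratory and too small to be informative in any case. This stands, and it is the main reason why the point is minor.

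A reader might go further and infer that the STI referral comparison is empty too. The documents do not support this. The arms get different procedures, and the referral procedures are not specified in detail. Most youth are mandated to the program for 15 days or less, while STI results may take up to 7 days after the sample is delivered. Failure to reach comparator youth is therefore plausible, and it would be a real arm difference in referral. More positives found and referred is also a genuine effect of a package meant to raise testing and linkage together.

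A reader might likewise expect a difference of about zero on 4(a) and 4(b). That holds among HIV-positive youth, but not for raw counts when test acceptance differs.

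**Conclusion.** The point holds in limited form. On the text as written, 4(a) and 4(b) cannot show linkage efficacy: among HIV-positive youth there is no contrast, and counts differ only through case finding. For STI the contrast is diluted by study-run contact and referral. Outcome 3(c) is a mixture of test uptake and referral, and is interpretable as a whole-package effect but not as a linkage effect.

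The size is small. HIV linkage is exploratory and STI linkage secondary. About 1 to 4 HIV-positive youth per arm would leave little to test under any protocol. None of the three primary outcomes is a linkage outcome, and the few youth concerned could not move them materially. The conclusion on HIV rests on the literal reading of one sentence. Every acceptance, positivity, referral and attendance rate used above is an assumption. Severity: minor.

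**What to change.** Leave all clinical procedures as they are; positives in both arms must be helped.

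1. Report 4(a) and 4(b) descriptively, pooled and by arm, with no arm test and no claim of linkage efficacy. If the HIV sentence was meant for Link2CARE only, limit it in the testing section and name the referral pathway for standard of care.
2. Keep 3(c) and 3(d), but analyse them per youth randomized. Interpret them as effects of the whole package (testing plus linkage) against study-run testing, notification and referral, and not as linkage effects alone.
3. Add a table by arm of youth tested, STI-positive, reached, referred and attended, so that case finding can be seen apart from linkage. Keep it descriptive, because STI-positive status arises after randomization.

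The cost is wording in the outcomes, testing and Aim 1 analysis sections, plus one reached/not-reached field. Sample size, staffing and care do not change. The one loss is an exploratory arm claim on HIV linkage.

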Analysis plan for Specific Aims 2 and 3. Descriptive statistics will be computed to quantify implementation at every step, by participant and by provider. Thus, we will be able to compute uptake of LINK2CARE, dose/intensity of intervention received, number of providers delivering each intervention, and other implementation parameters. Of note for Aim 2, which seeks to examine the proposed mechanisms of change of the intervention on HIV, STI and substance use outcomes, a given outcome (e.g. HIV/STI testing uptake, or PrEP uptake or reduced substance use) of this analysis will only be examined among those for whom it is relevant. For example, if a youth does not meet criteria for PrEP and as such is not offered PrEP, we would not include this youth in analyses of mechanisms of change of Link2CARE as they influence substance use or PrEP uptake as an outcome. We will examine the changes in specific outcomes (e.g. sexual behavior post-intervention) as a function of proposed theory-based intervention mediators (e.g. predisposing characteristics, enabling resources, perceived need for treatment/services). We will use structural equation models for these analyses. Structural equation modeling is preferred to multiple regression techniques because of the potential measurement error in our mediating variables and because of the possible feedback between dependent and mediating variables. We will test the model described in Figure 1 in the application, entering intervention condition as exogenous variables and the mediating factors included in Figure 1 as endogenous variables. Prior to conducting the structural analyses, however, we will examine the effects of the intervention on the putative mediating variables; a condition for inclusion in the equation will be a significant intervention effect on the potential mediators. Using standardized path coefficients, we will examine the relative associations of mediators to behavior change. We will also examine the path coefficient for the direct effect of the intervention after removing the effects of mediating constructs. For example, Link2CARE may have a more positive effect on acceptance of HIV (and STI) testing among JIY with greater perceived HIV risk, greater motivation to receive services, or positive HIV-testing history. Similarly, Link2CARE may have more positive effect on linkage outcomes when operating in an ASP that is more supportive of concepts perceived as innovative by both BIJ and STAY staff. Here, organizational culture would appear to modify Link2CARE's impact on youth service referral and engagement outcomes. We will examine the Lagrange Multiplier and Wald Tests to consider the deletion or inclusion of paths⁵; ultimately, however, deletion or inclusion of paths will be informed by theoretical underpinnings. Once the model is identified, we will test for group differences between intervention conditions in latent constructs and in the proposed paths between these constructs. This method will allow us to estimate the intervention effects on the constructs directly as well as their relationships to one another.⁶ We will use three goodness-of-fit indices: Bentler-Bonnet's Normed Fit Index, Bentler-Bonnet's Non-Normed Fit Index, and the Comparative Fit Index. We will also verify the root mean-square error of approximation (RMSEA) as an index of misfit. Well-fitting models will have fit indices of .90 or higher and $< .06$ for RMSEA.

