The aims of early interim analyses (in six-month intervals) are to (a) ensure that assumptions about mission-critical parameters (means, standard deviations, and prevalence of main outcomes) made for purposes of power are approximately correct; and (b) to monitor safety of the trial participants, reviewing all adverse events (AEs) and serious adverse events (SAEs). Interim analyses for safety and data monitoring of mission critical parameters, including recruitment and retention rates, will be conducted every 6 months by the trial statistician who will prepare the report for the PSMB (see Monitoring activities below). A third aim of interim analysis is (c) to check at a strategic point in the trial whether sufficiently strong evidence of positive or negative efficacy has accumulated to warrant consideration of stopping the trial (see Trial Stopping above). For all analyses the PI will remain blinded as to treatment assignments. As far as is feasible, the PSMB will also remain blinded, reviewing interim analyses prepared by the unblinded statistician in A/B format. They may, of course, request additional information for any safety concerns or risk-benefit analyses on an as-needed basis. Agreement on these procedures will be obtained with the PSMB prior to trial start. As described above, interim analyses for trial stopping will be conducted once after one-quarter of the 12-month data has been collected.

Monitoring activities

Although the Principal Investigator will have ultimate responsibility for reviewing conduct for the study and data emanating from it, including the reporting of any adverse events to the Institutional Review Boards of Columbia University/the New York State Psychiatric Institute (NYSPI) and NIDA, the PSMB will also review this project twice each year (every 6 months). The Principal Investigator will identify a list of adverse outcomes (e.g., significant psychological distress, loss of privacy) that might occur as a result of participation in the study. In

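### Covariates beyond gender are chosen by chance baseline imbalance, which leaves the fitted model open and forgoes precision for the two binary HIV-testing co-primaries

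*Combined protocol and SAP*

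**What the plan says.** The section on the analysis plan for Specific Aim 1 starts with a baseline screen, "testing for differences across demographic characteristics (e.g., race/ethnicity, age) using t-tests, ANOVAs, and Chi-squares, as appropriate". It says that systematic differences are not expected, but that "any parameters that differ across conditions at baseline will be included as covariates in subsequent models". It gives no significance level for deciding that a variable differs, and no closed list of variables to be screened.

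One covariate is fixed: "Stratified randomization of participants to the groups based on their gender requires that the analysis also include gender as covariate". The equation that follows is introduced with "The general form of the analysis model will be" and contains gender, group, time and group-by-time terms. Repeated outcomes use the "GEE method to account for within-subject correlation across the four time points (baseline, 3-, 6-, and 12-months"), so a baseline value enters as one of the repeated measurements and not as a covariate. On the target of inference the plan says: "The interaction coefficients δ_i are of interest, measuring the difference in the rate of change in outcome".

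The co-primaries are one count (unprotected sex occasions at 12 months) and two yes/no outcomes (acceptance of HIV testing when first offered; any HIV testing between 6 and 12 months). The section on sample size and power claims 80% power at a standardized effect of 0.35, with 169 per arm and a Bonferroni correction. It mentions no covariate adjustment.

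**The concern.** Under randomization, a baseline difference between arms says nothing about whether the variable predicts the outcome. A rule that adjusts for whatever differs will tend to leave out strong predictors that happen to be balanced, and may bring in irrelevant variables that happen not to be.

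This matters for the two yes/no co-primaries. Neither has a baseline measurement, so each reduces to a comparison of the arms at one point, adjusted for gender and whatever the screen flags. Three things follow.

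- The final model cannot be written down from the plan. For the 6-12 month testing outcome, which is also monitored, the flagged set could differ between the interim and final analyses.
- Under the logit link, each added prognostic covariate changes the odds ratio being estimated, so the reported effect depends on the baseline tests.
- Power that known predictors could supply is not collected.

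**Working it through.** **Inputs from the documents:** 450 randomized 1:1; 25% attrition, leaving 338, or 169 per arm; effect d = 0.35; two-sided alpha 0.05/3, so z = 2.394.

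**Assumed, because the documents are silent:** screening at 0.05; independent candidate variables; their number and prognostic strength; the control-arm rate of the binary outcomes.

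**1. The plan's own figure.** Power = Φ(d√(n/2) − z) = Φ(0.35 × √84.5 − 2.394) = Φ(3.217 − 2.394) = 79.5%. This agrees with the stated 80% and uses no covariates.

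**2. Chance that at least one variable enters.** 1 − 0.95^k gives 23% for k = 5, 40% for k = 10 and 64% for k = 20.

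**3. What fixed covariates could give, continuous approximation.** Adjustment multiplies the SD by √(1 − R²), so 3.217 becomes 3.217/√(1 − R²).

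| Assumed R² | Standardized shift | Power |
|---|---|---|
| 0 | 3.217 | 79.5% |
| 0.10 | 3.391 | 84.1% |
| 0.20 | 3.597 | 88.6% |
| 0.30 | 3.845 | 92.7% |

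**4. What the rule recovers for a binary outcome.** Logistic simulation, 4,000 trials per row, five prognostic covariates, treatment effect Cohen h = 0.35. Gender is left out for simplicity.

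| Per arm | Control rate | Log-odds per SD | No covariates | Plan's rule | All five fixed | Decision differs, rule vs fixed |
|---|---|---|---|---|---|---|
| 169 | 50% | 0.3 | 79.6% | 79.8% | 82.8% | 5.9% |
| 169 | 50% | 0.6 | 79.4% | 80.0% | 90.4% | 12.4% |
| 169 | 30% | 0.6 | 79.8% | 80.7% | 89.8% | 11.8% |
| 225 | 50% | 0.6 | 90.3% | 91.3% | 96.7% | 6.0% |

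The last row is relevant to acceptance at first offering, which is recorded at entry and so is not subject to 12-month attrition. The linear-model simulation agrees: with five covariates, the rule gives 79.1% and 80.4% at R² of 0.10 and 0.30, against 83.3% and 91.9% with fixed adjustment.

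**5. Type I error.** In the linear simulation under the null, with 5 or 10 covariates and R² of 0.10 to 0.30, the rule rejects in 1.2% to 1.45% of trials, against the nominal 1.67%. It is slightly conservative.

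**6. The odds ratio.** With a control rate of 50% and h = 0.35, the treated rate is sin²(arcsin√0.5 + 0.175) = 67.1%, so the unadjusted odds ratio is 0.671/0.329 = 2.04. Holding those two rates fixed, the conditional odds ratio is 2.07 to 2.16 with one covariate of 0.3 to 0.6 log-odds per SD, and 2.19 to 2.60 with five.

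**7. The count co-primary.** The tested term is the 12-month group-by-time interaction δ_3. A covariate that does not change over time and enters as a main effect contributes equally at every visit. With complete data it therefore drops out of the contrast between change in one arm and change in the other. Fitting the stated GEE with identity and log links, with and without five prognostic covariates, changed neither the estimate nor its standard error (differences of about 10⁻¹⁶). The plan imputes missing endpoints, so the analysed data sets are meant to be complete. Even with 25% missing at 12 months and no imputation, the standard error changed by only about 1%.

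**The case against.** The strongest reply is that nothing planned is harmed. The 80% power assumes no adjustment, the rule leaves power about there, and type I error is not inflated. What is lost is a gain that the plan never claimed, and its size rests on covariate strengths that the documents do not give. The named screening tests concern demographic characteristics, so the number of candidates may be nearer 5 than 20. One flagged covariate moves the log odds ratio by only about 2% to 8% (ln 2.07 or ln 2.16 over ln 2.04, before rounding), and the test of no effect is not affected by which odds ratio is estimated. All of this stands, and it sets the weight of the point.

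Four stronger readings are tempting but not supported.

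- *All three co-primaries are affected.* They are not; step 7 shows that the δ_3 contrast for the count outcome does not move. A gain there would need a different model form, which is a separate matter from this rule.
- *The printed equation contradicts the rule.* It is offered as a general form, to which the rule adds terms. Gender is already fixed in it.
- *Unblinding lets someone steer the selection.* The interim section does refer to "reviewing interim analyses prepared by the unblinded statistician in A/B format", but the rule uses baseline data only, and the principal investigator stays blinded.
- *The best predictors are already in hand.* The plan for Aims 2 and 3 mentions "positive HIV-testing history" and perceived HIV risk only as possible effect modifiers. The HIV behavioral risk screener is described only for the 225 Link2CARE youth, after randomization. No section shows that either item is measured at baseline in both arms.

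**Conclusion.** The concern holds for the two binary HIV-testing co-primaries, and for covariates other than gender. Their fitted model and conditional odds ratio depend on chance imbalance, and available precision is forgone. With 169 per arm, h = 0.35 and alpha 0.05/3, fixed adjustment would raise power from about 79-80% to about 83-90%, assuming five covariates of 0.3 to 0.6 log-odds per SD. Weaker predictors would give less. In those simulated trials the rule and fixed adjustment led to different significance decisions in about 6% to 12%.

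A reader might infer inflated error or a shortfall against the stated 80%; the calculations show neither. This is a cheap improvement in precision and prespecification, not a threat to validity.

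**What to change.** In the analysis plan for Specific Aim 1:

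- Delete the rule that adds variables differing at baseline, and report baseline balance descriptively, without tests.
- Before any unblinded look, fix one covariate set for the two binary co-primaries: gender, age, baseline substance-use frequency and baseline unprotected sex occasions. Add HIV-testing history and perceived HIV risk only if the sponsor confirms that they are measured before randomization or at baseline in both arms.
- Use the set unchanged at the final analysis and, for the monitored 6-12 month testing outcome, at the interim. A short list matters there: one quarter of 338 is about 84 participants.
- Keep adjustment for imbalanced variables as a sensitivity analysis only.

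The four core variables need only a wording change, because the plan already uses baseline values of both behavioral outcomes and age is an eligibility criterion. The two conditional items cost nothing more if they are already collected. The downside is that a variable outside the list that is imbalanced by chance is handled only in the sensitivity analysis.
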